### Scaling of the Sum of Target Lesions

Scaling of the sum of target lesion diameters is used when one or more target lesion diameter is missing because of on-study target lesion intervention.

If  $>1/3$  of target lesion measurements are missing (because of intervention) then target lesion response will be NE, unless the sum of diameters of non-missing target lesion would result in PD (ie, if using a value of 0 for missing lesions, the sum of diameters has still increased by  $> 20\%$  or more compared to nadir and the sum of target lesions has increased by  $\geq 5\text{mm}$  from nadir).

If  $\leq 1/3$  of the target lesion measurements are missing (because of intervention) then the results will be scaled up based on the sizes at the nadir visit to give an estimated sum of diameters and this will be used in calculations; this is equivalent to comparing the visit sum of diameters of the non-missing lesions to the nadir sum of diameters excluding the lesions with missing measurements.

### Example of Scaling

Lesion	Longest diameter (mm) at nadir visit	Longest diameter (mm) at follow-up visit
1	16	18
2	14	16
3	14	16
4	18	18
5	12	Intervention
Sum	74	68

Lesion 5 has had an intervention at the follow-up visit. The sum of the Baseline measures is 74 mm. The sum of lesions 1-4 at the follow-up is 68 mm. The sum of the corresponding lesions at nadir visit is 62 mm. Scale up as follows to give an estimated follow-up visit TL sum of 81mm:

$$\frac{68}{62} \times 74 = 81\text{mm}$$

### **Lesions that Split in Two or more Parts**

If a TL splits in two or more parts, then the LDs of the split lesions should be summed and reported as the LD for the lesion that split.

### **Lesions that Merge**

If two or more target lesions merge, then the LD of the merged lesion should be recorded for one of the TL sizes and the other TL sizes should be recorded as 0mm.

### **Change in Method of Assessment of Target Lesions**

CT and MRI are the only methods of assessment that can be used within this trial. If a change in method of assessment between CT and MRI occurs this will be considered acceptable and no adjustment within the programming is needed.

Note, if a change in method involves clinical examination (eg, CT changes to clinical examination or vice versa), any affected lesions should be treated as missing.

#### **3.1.1.2 Non-Target Lesions and New Lesions.**

At each visit an overall assessment of the NTL response should be recorded by the investigator. This section provides the definitions of the criteria used to determine and record overall response for NTL at the investigational site at each visit.

Non-target lesion response will be derived based on the Investigator's overall assessment of NTLs as follows:

**Table 3 NTL Visit Responses**

Visit Responses	Description
Complete response (CR)	Disappearance of all NTLs since baseline. All lymph nodes must be non-pathological in size (<10 mm short axis).
Non CR/non PD	Persistence of one or more NTLs with no evidence of progression.
Progression (PD)	Unequivocal progression of existing NTLs. Unequivocal progression may be due to an important progression in one lesion only or in several lesions. In all cases the progression MUST be clinically significant for the physician to consider changing (or stopping) therapy.
Not evaluable (NE)	Only relevant when one or some of the NTLs were not assessed and, in the Investigator's opinion, they are not able to provide an evaluable overall NTL assessment at this visit.  Note: for patients without TLs at baseline, this is relevant if any of the NTLs were not assessed at this visit and the progression criteria have not been met.
Not applicable (NA)	Only relevant if there are no NTLs at baseline.

CR: Complete response; NA: Not applicable; NE: Not evaluable; NTL non-target lesion; PD: Progressive disease; PR: Partial response; SD: Stable Disease; TL: target lesion

To achieve 'unequivocal progression' based on NTLs, there must be an overall level of substantial worsening in non-target disease such that, even in the presence of SD or PR in TLs, the overall tumor burden has increased sufficiently to merit a discontinuation of therapy. A modest 'increase' in the size of one or more NTLs is usually not sufficient to qualify for unequivocal progression status.

Details of any new lesions will also be recorded with the date of assessment. The presence of one or more new lesions is assessed as progression.

A lesion identified at a follow up assessment in an anatomical location that was not scanned at baseline is considered a new lesion and will indicate disease progression.

The finding of a new lesion should be unequivocal: ie, not attributable to differences in scanning technique, change in imaging modality or findings thought to represent something other than tumor.

New lesions will be identified via a Yes/No tick box. The absence and presence of new lesions at each visit should be listed alongside the TL and NTL visit responses.

A new lesion indicates progression, so the overall visit response will be PD irrespective of the TL and NTL response.

Symptomatic deterioration is not a descriptor for progression of NTLs: it is a reason for stopping study therapy and will not be included in any assessment of NTLs.

Patients with 'symptomatic deterioration' requiring discontinuation of treatment without objective evidence of disease progression at that time should continue to undergo tumor

assessments where possible until objective disease progression is observed.

### 3.1.1.3 Overall Visit Response

Table 4 defines how the previously defined TL and NTL visit responses will be combined with new lesion information to give an overall visit response.

**Table 4 Overall Visit Responses**

Target	Non-target	New Lesions	Overall Visit Response
CR	CR (or NA)	No (or NE)	CR
CR	Non-CR/Non-PD or NE	No (or NE)	PR
PR	Non-PD or NE or NA	No (or NE)	PR
SD	Non-PD or NE or NA	No (or NE)	SD
PD	Any	Any	PD
Any	PD	Any	PD
Any	Any	Yes	PD
NE	Non-PD or NE or NA	No (or NE)	NE
NA	CR	No (or NE)	CR
NA	Non-CR/Non-PD	No (or NE)	SD
NA	NE	No (or NE)	NE
NA	NA	No (or NE)	NED

CR complete response; PR partial response; SD stable disease; PD progression of disease; NE not evaluable; NA not applicable (only relevant if there were neither target nor non-target lesions at baseline); NED no evidence of disease.

## 3.2 Safety Variables

Safety and tolerability will be assessed in terms of AEs (including SAEs, AESIs, imAEs), deaths, physical examinations, laboratory data, vital signs, ECGs and exposure. These will be collected for all patients throughout the study.

### 3.2.1 Primary Safety Endpoint

The primary endpoint of this study is the incidence of Grade 3 and Grade 4 PRAEs (see Section 3.2.3.1) which occur within the first six months (ie, up to and including the 183rd day) after the initiation of durvalumab. Any Grade 3 or Grade 4 PRAEs which started after the 183rd day of the study, or after the 90th day following discontinuation of durvalumab, or after the start of subsequent anti-cancer therapy will not be included.

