The primary objective of this study is to assess the safety and tolerability of durvalumab which is defined as Grade 3 and Grade 4 possibly related adverse events (PRAEs), as assessed by the Investigator, observed within 6 months after the initiation of durvalumab treatment. In addition, safety and tolerability of durvalumab will be characterized for the cohorts of patients who received Standard Radiotherapy (60 Gy \pm 10% or hypofractionated BED) and patients who received palliative radiotherapy (40 to < 54 Gy or hypofractionated BED).

Safety data will be summarized descriptively overall, by seriousness, by causality and by maximum National Cancer Institute (NCI) Common Terminology Criteria for Adverse Events (CTCAE) Grade. The exact 95% confidence intervals (CIs) around the incidence of Grade 3 and Grade 4 PRAEs will be reported for patients overall and separately for each cohort.

The median PFS, median OS, and median time to NSCLC-related death, together with their corresponding 95% CIs, will be calculated using Kaplan-Meier product limit methods. The proportion of patients who are progression-free at 6 and 12 months and the proportion of patients who are alive at 12 months will be presented. In addition, the objective response rate (ORR), based on Investigator assessments, together with the corresponding 95% CIs will be reported.

[figure not shown]
A total of approximately 102 patients are treated with the study drug in 2 cohorts: approximately 59 patients in the Standard Radiotherapy Cohort and approximately 43 patients in the Palliative Radiotherapy Cohort. It is estimated that a sample size of a minimum 60 patients would be required to provide an adequate level of confidence in the estimated incidence of Grade 3 and 4

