8.3.2 Time period and frequency for collecting AE and SAE information

AEs and SAEs will be collected from the time of the patient signing the ICF until 90 days after the last dose of durvalumab. If an event that starts after the defined safety follow-up period noted above is considered to be due to a late onset toxicity to study drug, then it should be reported as an AE or SAE as applicable.

All SAEs will be recorded and reported to the Sponsor or designee within 24 hours, as indicated in [Appendix B](#). The Investigator will submit any updated SAE data to the Sponsor within 24 hours of it being available.

Investigators are not obligated to actively seek AEs or SAEs in former study patients. However, if the Investigator learns of any SAE, including a death, at any time after a patient's last visit and he/she considers the event to be reasonably related to the study treatment or study participation, the Investigator should notify the Sponsor.

The method of recording, evaluating, and assessing causality of AEs and SAEs and the procedures for completing and transmitting SAE reports are provided in [Appendix B](#).

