9.5 Statistical analyses

Descriptive statistics will be used for all variables. Continuous variables will be summarized by the number of observations (n), mean, standard deviation, median, quartiles (Q1 and Q3), minimum, and maximum. Categorical variables will be summarized by frequency counts and percentages for each category.

For all summaries of AEs, only treatment-emergent AEs will be included. Treatment-emergent AEs are defined as events present at baseline that worsen in intensity after administration of IP or events absent at baseline that emerge after administration of IP, for the period extending to 90 days after the last dose of IP. Baseline will be the last assessment of the variable under consideration prior to the first IP dose administration.

A data analysis is planned to be performed once all patients had the opportunity to receive treatment for 6 months, ie, the DCO for this primary analysis would be expected 6 months after the last patient has received first dose of durvalumab. The data from this analysis would be published to support the real-world use of durvalumab.

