9.5.2 Analysis of the secondary variables

9.5.2.1 Safety variables

Adverse events

Total SAEs, AESIs, AEs leading to death, and AEs leading to study drug interruption or discontinuation will be summarized by Medical Dictionary for Regulatory Activities (MedDRA) by system organ class and preferred term, causality, and maximum NCI CTCAE Grade. Deaths from all causes will be also summarized.

Data from all cycles of will be combined in the presentation of safety data. AEs (both in terms of MedDRA preferred term and CTCAE Grade) will be listed individually by patient. Any AE occurring before treatment with IP will be included in the data listings but will not be included in the summary tables of AEs. Any AE occurring within 90 days of discontinuation of IP may be included in the AE summaries, but the majority of the AE summaries will omit the AEs observed after a patient has received further therapy for cancer. Further details will be provided in the SAP. Any AE that occurs after a patient has received further therapy for cancer (following discontinuation of IP) will be flagged in the data listings.

A separate data listing of AEs occurring more than 90 days after discontinuation of IP will be produced. These events will not be included in AE summaries.

For the change from baseline summaries for vital signs, laboratory data, ECGs, and physical examination, the baseline value will be the latest result obtained prior to the first IP dose administration.

The QTcF will be derived during creation of the reporting database using the reported ECG values (RR and QT) using the following formula:

$$\text{QTcF} = \text{QT}/\text{RR}^{(1/3)} \text{ where RR is in seconds}$$

Corrected calcium product will be derived during creation of the reporting database using the following formula:

$$\text{Corrected calcium (mmol/L)} = \text{Total calcium (mmol/L)} + ([40 - \text{Albumin (G/L)}] \times 0.02)$$

The denominator used in laboratory summaries will include only evaluable patients, ie, those who had sufficient data to have the possibility of an abnormality, for example:

- If a CTCAE criterion involves a change from baseline, evaluable patients would have both a predose and at least one postdose value recorded.
- If a CTCAE criterion does not consider changes from baseline, to be evaluable, the patient need only have one postdose value recorded.

The denominator in vital signs data should include only those patients with recorded data.

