### **3.2.3 Adverse Events**

AEs and SAEs will be collected throughout the study, from time of the patient signing the informed consent and 90 days after the last dose of durvalumab. A treatment emergent adverse event (TEAE) is an AE with an onset date or a pre-existing AE worsening following the first dose of study treatment through to 90 days after the last dose of durvalumab.

The Medical Dictionary for Regulatory Activities (MedDRA) (using the latest or current MedDRA version) will be used to code the AEs. AEs will be graded according to the National Cancer Institute Common Terminology Criteria for AEs (CTCAE Version 5.0). The meaning of these categories are as follows:

- Grade 1: Mild AE
- Grade 2: Moderate AE
- Grade 3: Severe AE
- Grade 4: Life-threatening or disabling AE
- Grade 5: Death related to AE

Any TEAE will be included in the AE summaries as detailed in Section 4.5.1.

Missing start and stop dates for AEs will be imputed using the rules described in Section 4.1.3.

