#### **3.2.3.1 Possibly-Related Adverse Events**

A PRAE is any TEAE with a relatedness to durvalumab of possible, or where the relatedness is missing. When the relatedness of a TEAE is missing on the electronic Case Report Form (eCRF), all efforts will be taken to ensure that the Investigator assigns his/her assessment of relatedness prior to DBL.

If relatedness of a TEAE is missing at the DBL, as given in Section 4.1.2, the TEAE will be considered as possibly related to durvalumab.

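### The six-month primary count leaves out Grade 3/4 related events that start after new anti-cancer therapy, and no planned table gives the rate with them included

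*SAP*

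**What the plan says.** **Protocol, endpoint and analysis.** The Synopsis and Section 9.2 define the primary endpoint as Grade 3 and 4 PRAEs "observed within 6 months after the initiation of durvalumab treatment". Neither they nor Section 9.5.1 (primary variable) mention later anti-cancer therapy. Section 9.5 limits every AE summary to treatment-emergent events, "for the period extending to 90 days after the last dose of IP". Section 9.5.2.1, under secondary safety variables, says that most AE summaries will omit events seen after further cancer therapy and leaves the detail to the SAP. For events later than 90 days it states "A separate data listing of AEs occurring more than 90 days after discontinuation of IP will be produced", and keeps them out of the summaries.

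**SAP.** Section 3.2.1, repeated in 4.3, takes "Grade 3 and Grade 4 PRAEs (see Section 3.2.3.1) which occur within the first six months (ie, up to and including the" 183rd day. It then removes events starting after the 90th "day following discontinuation of durvalumab, or after the start of subsequent anti-cancer therapy will not be included". Section 4.3 gives the percentage with a Clopper-Pearson interval in the full Safety Analysis Set (SAF), overall and by cohort. Section 3.2.3.1 says "A PRAE is any TEAE with a relatedness to durvalumab of possible, or where the relatedness is missing", and Section 3.2.3 runs the treatment-emergent period "following the first dose of study treatment through to 90 days after the last dose of durvalumab". Section 4.5.1 adds a table by system organ class and preferred term of PRAEs starting within 90 days of the last dose whatever therapy followed. The legible text of Section 6 does not list the new-therapy exclusion as a change.

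**Collection.** Protocol 4.1 and the Synopsis include patients who have begun other anti-cancer therapy among those followed for AEs for 90 days after stopping. Table 2 schedules AE assessments at 30 days, 2 months and 3 months after the last dose. Under Section 8.3.2, an event starting later that is "considered to be due to a late onset toxicity to study drug, then it should be reported as an AE or SAE", but sites need not look for events in former patients.

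**The concern.** Related Grade 3/4 events after a switch of therapy, but within 90 days of the last dose, are collected at scheduled visits and assessed for causality. The primary count then drops them, although the protocol describes the endpoint by grade, relatedness and time from first dose only.

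The denominator stays at the full SAF, with no censoring or at-risk adjustment. A patient whose only qualifying event falls after new therapy is therefore scored as event-free, so the exclusion can move the rate in one direction only. At stake is the main safety estimate, and more so the cohort estimates, where one patient counts for more. A reader of the report would have no six-month Grade 3/4 figure from which to judge whether the exclusion mattered.

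**Working it through.** **1. The plan's own figures.** Clopper-Pearson at x = n × p, allowing non-integer x, reproduces the 12% column of SAP Table 1: 7.2/60 gives 5.0-23.0% (±9.0), and 3.6/30 gives 3.1-29.1% (±13.0). With a whole count, 7/60 gives 4.8-22.6%. The point below does not depend on these figures.

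**2. Reach of the new-therapy exclusion.** Let the last dose fall on Day d and new therapy start on Day s. The onset days excluded although they lie inside both the six-month window and active follow-up number min(183, d + 90) − s. As an illustration with assumed days, d = 57 and s = 85 gives 147 − 85 = 62 days (Days 86 to 147). The exclusion can reach any patient who starts other therapy before Day 183.

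**3. Reach of the 90-day limit.** Excluded onset days run from d + 91 to 183, which is 93 − d days. On nominal four-weekly dosing:
- last dose Day 1: 92 days
- Day 29: 64 days
- Day 57: 36 days
- Day 85: 8 days
- Day 113 or later: none

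Only patients who stop after one to four doses can be affected.

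**4. Effect per patient with only an excluded event** (N from SAP 1.3; starting counts chosen near 12%; exact 95% intervals).
- Overall: 12/102 = 11.8% (6.2-19.6); 13/102 = 12.7% (7.0-20.8). Step 1/102 = 1.0 point.
- Standard cohort: 7/59 = 11.9% (4.9-22.9); 8/59 = 13.6% (6.0-25.0). Step 1/59 = 1.7 points.
- Palliative cohort: 5/43 = 11.6% (3.9-25.1); 6/43 = 14.0% (5.3-27.9). Step 1/43 = 2.3 points.

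**5. How many patients.** The documents give neither a switching rate nor a late-event rate for this trial, so both ranges below are assumptions.
- Both exclusions together: suppose 10-30% of patients stop early or switch, and 2-10% of those have only an excluded event. Then 102 × 0.10 × 0.02 = 0.2 and 102 × 0.30 × 0.10 = 3.1 patients, a shift of 0.2 to 3.0 points.
- 90-day limit alone: suppose 15-35% stop after one to four doses, with a mean loss of (92 + 64 + 36 + 8)/4 = 50 days. Take the on-drug hazard as −ln(0.88)/183 per day and the off-drug hazard as 25-100% of it. Then 102 × share × 50 × [−ln(0.88)/183] × ratio gives 0.13 to 1.25 events. This counts events occurring, not events reported. It also does not remove patients who already have a qualifying event, have died or have withdrawn.

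**6. What the planned tables offer.** The SAP 4.3 table has the right grades, window and interval, but applies the exclusion. The SAP 4.5.1 table ignores later therapy, but covers all grades by preferred term, with no six-month window and no stated interval. Neither gives the six-month Grade 3/4 rate irrespective of new therapy.

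**The case against.** The exclusion can be defended. Protocol 4.2.2 expects that patients may later receive other PD-1/PD-L1 agents, so attribution to durvalumab is less certain after a switch. Protocol 9.5.2.1 foreshadows the omission and hands the detail to the SAP. A patient with an earlier qualifying event loses nothing. The trial is single-arm and descriptive, with no threshold for a shift to cross, and a point or two is small beside an interval of 6.2-19.6%. All of this stands, and it is why the primary definition need not change. It does not supply the missing estimate.

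Three stronger readings are tempting, and the documents do not support them.
- A reader might infer that the SAP deletes late-onset toxicity that Protocol 8.3.2 asks sites to report. The 90-day limit is the protocol's own: Section 9.5 applies it to all AE summaries, 9.5.2.1 sends later events to a listing, and SAP 3.2.3 and 3.2.3.1 carry it through. An event beyond 90 days is not a PRAE under either document.
- A reader might infer that every dropped PRAE was judged drug-related by an investigator. PRAEs also include events with missing relatedness.
- A reader might infer a bias concentrated in patients prone to toxicity, or in the palliative cohort. Patients who stopped for a related Grade 3/4 event with onset before any new therapy are already counted, and the documents give no stopping rates by cohort.

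**Conclusion.** The point holds for the new-therapy exclusion. It removes actively collected events from inside the six-month window, it can only lower the rate, and no planned table shows the rate without it. Each affected patient is worth 1.0 point overall, 1.7 in the standard cohort and 2.3 in the palliative cohort, at the planned sizes.

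The number affected is unknown. Under the assumed ranges, both exclusions together cost 0.2 to 3.0 points overall, and no separate figure for the new-therapy exclusion can be derived from the documents. The 90-day limit follows the protocol, matters only for patients who stop after one to four doses with no earlier qualifying event, and has a small effect that rests on assumptions. This is a low-cost gain in transparency. It does not invalidate the primary endpoint.

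**What to change.** Keep the primary definition. In SAP 4.3, pre-specify:
- A supplementary row, overall and by cohort with exact Clopper-Pearson 95% intervals, counting patients with a Grade 3/4 PRAE with onset from first dose to Day 183 and within 90 days of the last dose, irrespective of subsequent anti-cancer therapy.
- By cohort, the number of patients whose only qualifying event was excluded by the new-therapy rule.
- Separately by cohort, the number whose only reported related Grade 3/4 event by Day 183 fell outside the 90-day limit.
- Identification of events counted as related only because causality is missing.

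State one anchor for the 90 days: SAP 3.2.1 and 4.3 use discontinuation, while 3.2.3 uses last dose.

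The cost is one extra row and a few counts from data already collected. Attribution is less certain after a switch, so the row should be labelled supplementary. A footnote should say that capture beyond 90 days is passive. Moving those later events into the primary count itself would mix active and passive capture over a fixed denominator and depart from Protocol 9.5, so it is not proposed.
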